3.2. Effectiveness analyses

3.2.1. Effectiveness analyses

Primary outcome

Relative risk of death in-hospital (within 30d) in the intervention arm vs death in-hospital (within 30d) in the standard of care arm, estimated by univariable generalised estimating equation under a binomial model with a log link and assuming an exchangeable correlation structure. Clustering will be assumed to be on hospitals within countries in a fully nested framework.

Secondary outcome

Relative risk of death in-hospital or severe complication (within 30d) in the intervention arm vs death in-hospital or severe complication (within 30d) in the standard of care arm. Analysis approach will be as in primary outcome.

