6.3. Randomisation

Participating sites will be randomised to normal postoperative care (“SOC”), or increased postoperative surveillance (“Intervention”) in four recruitment blocks (calendar time blocks). Randomisation in each block will be stratified by country and by level of the surgical facility with a fixed block size of 2. The randomisation algorithm will seek to balance randomisation arms by simulating randomisations with an automated filter to screen out poorly balanced randomisations. In the second and subsequent recruitment blocks, the randomisation algorithm will use knowledge of the previous randomisations and a similar simulation and filtering approach to ensure reasonable balance across arms and across level of surgical facility. This approach was developed on the basis of a simulation model for the randomisation that was used to evaluate the probability of overall balance of randomisation arms and balance within level of care strata if randomising recruitment phases in waves. Results of 10,000 simulation runs indicated that a balanced simulation within the bounds described below would be obtained >50% of the time without the filtering step.

The algorithm is described briefly here:

For recruitment phase 1:

1. Simulate stratified block randomisation within country and level of facility
2. Check that simulated randomisation has percent SOC between [48% - 52%]
3. If NO, then repeat steps 1 and 2. If YES then use this randomisation.

For all other recruitment phases:

1. Simulate stratified block randomisation for this phase within country and level of facility
2. Combine this simulation with prior actual randomisations
3. Check that combined randomisation has percent SOC between [48% - 52%]
4. If NO, then repeat steps 1-3. If YES proceed to next check.
5. Check that combined randomisation has balance within level of care between [45% - 55%]
6. If NO, then repeat steps 1-5. If YES then use this randomisation.

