7.2. Statistical analysis

Outcomes will be presented at a continental level. All institutional level data will be anonymised prior to publication. Categorical variables will be described as proportions and will be compared using chi-square tests. Continuous variables will be described as mean and standard deviation if normally distributed or median and inter-quartile range if not normally distributed. Comparisons of continuous variables between groups will be performed using t-tests, one-way ANOVA or equivalent non-parametric tests as appropriate.

The primary outcome will be in hospital mortality. Overall differences in in-hospital mortality will be compared between the intervention and control clusters. All analyses will account for clusters. A list of baseline risk factors (the risk factors in the ASOS Surgical Risk Calculator) will be included in the analysis. We will use logistic regression model to estimate the effect of increased postoperative surveillance, on the primary and secondary outcomes. We will calculate the odds ratios and their associated 95% confidence intervals. We will infer statistical significance if the computed 2-sided p-value is < 0.05 . A single final analysis is planned at the end of the study.

The detailed statistical analysis plan was added on 19 March 2020 and is attached as Appendix 6 to this document.

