3.2.3. Patient risk factors and patient level analysis

A prespecified patient level analysis will be undertaken including all high-risk individuals with data in a standard of care hospital, and all high-risk individuals in an intervention arm who can be presumed to be exposed to the intervention (definition 1: poster and one other intervention on day 0 and day 1; definition 2: any 2 interventions on day 0 and day 1). The relative risk of experiencing the primary (secondary) outcome by exposure to intervention (as defined above) will be estimated in stratified models for the following individual characteristics:

- I. age (years)
- II. ASA status (1-5)
- III. surgical procedure category (Gynaecologic, Obstetric, Neuro, ENT, Orthopaedic, Plastics and Breast, Urology, Gastrointestinal and Hepatobiliary, Cardiothoracics, Other)
- IV. indication for surgery (non-communicable disease, caesarean section, trauma, infection)
- V. urgency of surgery (elective, urgent, emergent)
- VI. severity of surgery (minor, intermediate, major)

This concludes the pre-specified analyses for ASOS-2. Further exploration of the data will take place.

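### Protocol 7.2 and SAP 3.2.1 give different primary models without saying which governs, and the SAP model omits the randomisation strata and does not name its variance unit

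*Combined protocol and SAP*

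**What the plan says.** **Protocol 7.2.** "We will use logistic regression model to estimate the effect of increased postoperative surveillance, on the primary and secondary outcomes". On covariates: "A list of baseline risk factors (the risk factors in the ASOS Surgical Risk Calculator) will be included in the analysis". Results are odds ratios with 95% intervals, and clustering is to be accounted for by a method that is not named. The only link to the SAP is that "The detailed statistical analysis plan was added on 19 March 2020" and is attached as Appendix 6.

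**SAP 3.2.1.** The primary outcome is a relative risk, "estimated by univariable generalised estimating equation under a binomial model with a log link and assuming an exchangeable correlation structure". On clustering: "Clustering will be assumed to be on hospitals within countries in a fully nested framework". The secondary outcome follows the same approach. SAP 3.2.3 ends: "This concludes the pre-specified analyses for ASOS-2".

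**Randomisation.** Protocol 6.3 randomises hospitals in four calendar-time recruitment blocks: "Randomisation in each block will be stratified by country and by level of the surgical facility with a fixed block size of 2". SAP 3.1 describes stratification by hospital level, carried out in waves, and does not mention country. Protocol 5.2 names facility level and case load. Protocol 7.1 speaks of matching on weekly volume and of stratifying by level and volume. In SAP 3.2.2, level and calendar quarter appear only as subgroup variables.

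**The concern.** The two sections differ in link, effect measure and covariates. A risk-adjusted test and an unadjusted test of the same data can fall on opposite sides of p = 0.05, so the text should say once which is confirmatory. The SAP was added in the month that recruitment was due to end, so a reader cannot treat 7.2 as an early sketch long since replaced.

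The SAP model also does not reflect the design. Stratified randomisation makes the arms more alike on the stratifiers. A model without them does not credit that balance, so its standard error is too large if the strata predict mortality. The SAP has no adjusted comparison of the arms as randomised: the models in 3.2.3 are limited to high-risk patients and, in the intervention arm, to those presumed exposed.

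Finally, an exchangeable GEE has one clustering level, while the nesting sentence names two. An analyst could code the robust variance over hospitals or over countries, and the two behave differently when countries are few.

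**Working it through.** **1. Plan's own figure.** Inputs from protocol 7.1 and Table 1: 2.0% vs 1.5%, ICC 0.015, CV 0.63, mean cluster size 100, 80% power, two-sided 0.05.

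- Patients per arm before clustering: (1.960 + 0.842)² × (0.02 × 0.98 + 0.015 × 0.985) / 0.005² = about 10,792.
- Design effect: 1 + ((1 + 0.63²) × 100 − 1) × 0.015 = 1 + 138.69 × 0.015 = 3.080.
- Clusters: 2 × 10,792 × 3.080 / 100 = 664.9, against 664 stated. The other rows give 536.4 (536 stated) and 1068.2 (1068 stated).

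The sample size is therefore an unadjusted comparison with hospital as the cluster. It reproduces, and it is not at issue.

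**2. Effect measure.** At 2.0% vs 1.5%, RR = 0.75 and OR = (0.015/0.985)/(0.020/0.980) = 0.746. For mortality the scale hardly matters; the covariates are the real difference. How far patient-level risk adjustment would move the p-value cannot be computed, because the documents do not give its prognostic strength.

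**3. Omitted strata, by formula.** Let R be the share of between-hospital variance that the strata explain (assumed; the documents give none), and suppose the strata are perfectly balanced. Then DE(R) = 1 + 138.69 × ICC × (1 − R), and SE(R) = √(0.034375 × DE(R) / 33,200). The univariable test uses SE(0) while the true value is SE(R).

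- Type I error = 2 × (1 − Φ(1.96 × SE(0)/SE(R))).
- Univariable power = Φ((0.005 − 1.96 × SE(0))/SE(R)).
- Adjusted power = Φ(0.005/SE(R) − 1.96).

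Example at R = 20%: SE(0) = 0.001786 and SE(R) = 0.001661. Type I error is 2 × (1 − Φ(2.107)) = 3.5%, and power is Φ(0.903) = 81.7% univariable vs Φ(1.050) = 85.3% adjusted.

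| R (ICC 0.015) | DE | Type I | Interval too wide by | Power, univariable | Power, adjusted |
|---|---|---|---|---|---|
| 10% | 2.87 | 4.2% | 3.6% | 80.8% | 82.6% |
| 20% | 2.66 | 3.5% | 7.5% | 81.7% | 85.3% |
| 30% | 2.46 | 2.8% | 12.0% | 82.7% | 88.0% |

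At ICC 0.01, the value seen in ASOS, the gains are 1.0, 2.0 and 2.8 points. For each share these figures are upper bounds, because balance will not be complete: with an assumed 25 countries × 3 levels × 4 waves there are 664/300 = 2.2 hospitals per cell.

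**4. Omitted strata, by simulation.** Settings: 664 hospitals; gamma sizes (mean 100, CV 0.63); 2% control mortality; 25 uneven countries (the ASOS number, assumed for ASOS-2); strata share split half country, quarter level, quarter wave. Blocks of 2 are drawn within country, level and wave, with the 48–52% and 45–55% filters applied to the complete allocation. Weights are hospital-exchangeable. The adjusted model pools countries with fewer than 10 hospitals into two groups and corrects the variance for leverage.

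| R (ICC 0.015) | Type I, univariable, hospital unit | Type I, adjusted | Power, univariable | Power, adjusted | Change in points |
|---|---|---|---|---|---|
| 0% | 4.4% | 4.6% | 86.8% | 86.2% | −0.6 |
| 10% | 4.6% | 5.1% | 88.3% | 88.9% | +0.6 |
| 20% | 4.2% | 5.2% | 89.0% | 90.9% | +1.9 |
| 30% | 3.5% | 4.8% | 88.8% | 92.2% | +3.4 |

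At ICC 0.01 the gains are 0.0, 1.0 and 2.0 points. The Monte Carlo error of each type I figure is about 0.3 points, so only the 30% row differs clearly from the 0% row. Power exceeds the formula mainly because exchangeable weights are more efficient than patient-count weights. Without the variance correction, the adjusted model's type I error is 5.1% to 5.8%.

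**5. Variance unit.** In the same simulation, the univariable model with country as the unit has type I error of 7.4% to 8.5% against a normal reference and 6.1% to 6.9% against t with 24 degrees of freedom. A separate simulation with other assumed country, level and wave effects, and no balance filter, gives 6.5% to 7.1% with 25 countries and 8.3% to 9.6% with 12. With the hospital unit and 25 countries it gives 4.5% down to 1.3%, the low end under the strongest assumed country and level effects.

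**The case against.** The documents largely settle which model governs: 7.2 defers to the later, more detailed plan, and the SAP describes its own list as the complete set of prespecified analyses. This stands, so the first part mostly needs one clarifying sentence. A reader might infer that two confirmatory models are wholly unresolved, or that the model was changed after the results were seen. The documents support neither; they give a date for the SAP and say nothing about access to results.

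Hospital is also the natural cluster. The summary and protocol 7.1 count and define clusters as hospitals or surgical sites. This stands too, so country-level variance is the less likely reading. The SAP sentence still permits it, and one clause would exclude it.

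Stratum adjustment can be called an efficiency preference resting on assumed shares. That is fair as to size: the gains are small, could be nil, and turn into a small loss if the strata are not prognostic. It does not remove the reason to analyse by the groups used in the randomisation.

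A further objection is that fixing country, level and wave as the model terms would prejudge the conflict over volume or case load. This is right, so the terms must follow the randomisation actually used.

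**Conclusion.** The concern holds in a limited form. The model conflict is real on the page but mainly needs clarifying. The missing strata and the unnamed variance unit are specific gaps that cost little to close.

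A reader might go further and infer that omitting the strata biases the estimate, inflates type I error or forfeits the planned power. None of this follows. With hospital as the unit the test keeps or falls below its nominal 5%, and the planned 80% power is not lost. The likely cost is mild conservatism: roughly 0 to 3.4 points of power forgone for assumed shares of 10% to 30%. The formula's 2.8% to 4.2% type I error and 3.6% to 12.0% excess interval width should be read as bounds under full balance, not as expected values.

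Type I error rises above 5%, to about 6% to 8.5%, only if country is taken as the unit, and that range rests on an assumed 25 countries. The textual findings are firm; the magnitudes depend on strata shares and a country count that the documents do not give for ASOS-2.

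**What to change.** 1. State in protocol 7.2 that SAP 3.2.1 supersedes the model described there.
2. In SAP 3.2.1, name hospital as both the cluster and the unit of the robust variance, with exchangeable correlation within hospital.
3. Make protocol 5.2, 6.3 and 7.1 and SAP 3.1 agree with the randomisation actually used.
4. Put the strata actually used into the log-link GEE for both outcomes. By protocol 6.3 these are level, wave and country; add volume if it was used. Pool sparse countries by a rule fixed before outcomes are compared by arm; the income categories in SAP 3.2.2 are one available grouping. Specify a small-sample variance correction, such as a leverage correction, and a modified Poisson fallback with the same terms if the log-binomial fit does not converge.
5. Report the univariable relative risk as a sensitivity analysis, so that the SAP's current estimate stays visible.

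The cost is a sentence or two in 7.2, a revised 3.2.1, reconciled strata text and a few lines of code. By protocol 6.3, level, country and wave are known for every randomised hospital. The downsides are possible non-convergence, the pooling of sparse countries, and about 0.6 points of power if the strata prove not to be prognostic. The revision should be dated and made before any comparison by arm, so that it does not itself raise a question of prespecification.

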3.2.2. Sensitivity and subgroup analyses on the effectiveness outcomes

Sensitivity analysis will investigate the potential for unobserved outcomes (transfer out or lost to follow up) to impact primary and secondary effectiveness estimates. Under the same model as the primary (secondary) effectiveness outcomes individuals with unobserved outcomes (lost to follow up) will alternately be assumed to be alive at discharge (censored at thirty days) or to have died in-hospital within 30 days. These estimates and confidence intervals will be plotted along with the primary (secondary) effectiveness estimates.

Primary and secondary endpoints will be analysed under the same model as the primary analysis for the following subgroups treated as stratification variables:

- i) hospital level (primary, secondary, tertiary),
- ii) duration of recruitment (1, 2, 3 or 4 weeks)
- iii) Calendar time (quarters)
- iv) Income category of country (low or middle, according to the World Bank classification in 2020)

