Statistical analysis	The primary outcome measure is in-hospital mortality censored at 30 days of randomisation. The analysis will be conducted according to intention-to-treat principles; all participants with a recorded outcome will be analysed according to the treatment group to which they were randomised.
Recruitment start date	May 2019
Recruitment end date	March 2020
Trial duration	Until hospital discharge, censored at 30 days

3. Introduction

The non-cardiac surgical population represents a major global public health burden with approximately 234 million major surgical procedures performed worldwide each year.¹ In unselected non-cardiac surgical patients, reports of early postoperative mortality vary between 2 and 4%,^{2,3} with an annual global mortality of 5 to 10 million. Surgery is a cost-effective intervention,⁴ even in low to middle income countries⁵ and as such it is considered a core component of health.⁶ The Lancet Commission on Global Surgery was established to define safe surgery and develop strategies to ensure the adequate provision of safe surgery.⁷

Recently, the African Surgical Outcomes Study (ASOS) demonstrated, that despite a patient low risk profile and low complication rates, patients in Africa were twice as likely to die following surgery when compared to the global average.⁸ ASOS provides the most comprehensive data on surgical outcomes in Africa, comprising 25 countries, 247 hospitals, and data from over 11 000 patients.⁸ Importantly, 95% of the deaths in ASOS occurred in the postoperative period, suggesting that many lives could be saved by effective surveillance for physiological deterioration amongst the patients who developed complications.⁸ In ASOS, the median number of combined anaesthesia, surgical and obstetric specialists was 0.7 (IQR 0.2-1.9) per 100,000 population,⁸ which is well below the documented inflection point of 20 to 40 specialists per 100,000 population necessary to significantly decrease surgical mortality.⁷

It is likely that a major contributor to the high mortality in ASOS was 'failure to rescue' after a postoperative complication partly due to an inadequacy of sufficient human resources necessary to identify postoperative surgical patients at risk. A potential solution to improving surgical outcomes in Africa is identification of the high-risk surgical patient prior to further physiological deterioration.

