6.5. Data collection and collation

Dataset

This is a pragmatic trial in a resource-limited environment. As a result, a realistic data set will be fundamental to the success of the trial. We are confident that the proposed data set will achieve this objective, as it is smaller than the data sets used in ASOS,⁸ the European Surgical Outcomes Study (EuSOS),³ and the International Surgical Outcomes Study (ISOS),¹⁰ and these studies successfully achieved follow up on >95% of patients despite requiring data on all surgical patients at each participating centre for a week of surgery. We believe that these key data points will encourage centres to participate as there will not be an excessive burden of data collection.

Centre-specific data will be collected once for each hospital including: university or non-university hospital, number of hospital beds, number of operating rooms, number and level of critical care beds and details about the reimbursement status of the hospital.

An ASOS-2 case record form (CRF) will be completed for every eligible patient who undergoes surgery during the trial (appendix 3). Patients will be followed up until hospital discharge. This will be censored at thirty days i.e. patients will be followed up until discharge or for thirty days whichever is the shorter period.

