4. Radiological or echocardiographic evidence of new loss of viable myocardium or new regional wall motion abnormality
5. Identification of an intra-coronary thrombus at angiography or autopsy

Pulmonary embolism (PE)

A new blood clot or thrombus within the pulmonary arterial system.

Guidance: Appropriate diagnostic tests include scintigraphy and CT angiography. Plasma D-dimer measurement is not recommended as a diagnostic test in the first three weeks following surgery.

Stroke

Embolic, thrombotic, or haemorrhagic cerebral event with persistent residual motor, sensory, or cognitive dysfunction (e.g. hemiplegia, hemiparesis, aphasia, sensory deficit, impaired memory).

Hospital resource use after surgery

We will collect some basic data to describe the treatment resources patients received after surgery.

Critical care admission to treat postoperative complications:

Postoperative complications requiring admission to critical care to treat the postoperative complications or provide critical care support necessitated by the severity of the postoperative complications.

Days in hospital after surgery: Total number of days in hospital after surgery.

Status at hospital discharge or 30th postoperative in-hospital day: The survival status of the patient at hospital discharge, or at the 30 in-hospital day (if the patient had not yet been discharged following surgery). The study is censored at the 30th in hospital postoperative day.

Reference

Appendix 2

African Surgical OutcomeS-2 (ASOS-2) Trial: Hospital 'broadcasting' signage

IMPORTANT PATIENT INFORMATION

A research study is being conducted atHospital.

The research is being done by Dr from the Department of

Why is this research study being done?

To understand if increasing monitoring following surgery, makes surgery safer.

Why are we telling you about this study?

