Higher care ward No YesIncreased nursing observations No YesAssigned a bed in view of nurses' station No YesFamily with patient in ward No YesSevere complications (tick all that apply): Superficial or deep surgical site, or body cavity infection N Y Postop day Bloodstream infection or ARDS N Y Postop day Pneumonia N Y Postop day Urinary tract or AKI N Y Postop day Postoperative bleed N Y Postop day Cardiac arrest N Y Postop day Other severe complication N Y Postop day Days in hospital after surgery Status at hospital discharge or 30th postoperative in-hospital day: Alive & still in hospital Dead Alive & discharged → if alive and discharged, was patient transferred to another facility for higher care? Yes NoIf deceased, photo of clinical note of death uploaded: Yes CRF completed and verified by..... on dd/mm/2019ASOS-2 unique patient ID

ASOS-2 Trial CRF v4 (Control arm)

Patient name: _____

DOB d m y y y Patient hospital number : _____ ASOS-2 unique patient ID

African Surgical OutcomeS-2 (ASOS-2) Trial: Case Record Form (CRF) (Intervention arm)

Age years (<30 points; 0 points/ 30-69 years; 1 point/ ≥70 years; 3 points) Sex M F

ASA I (0 points) II (2 points) III (5 points) IV (8 points) V (8 points)

Chronic co-morbid disease (tick all that apply): Hypertension HIV / AIDS Diabetes mellitus COPD / Asthma

Surgical procedure category (select single most appropriate): Gynaecology (minus 1 point) Obstetrics (minus 1 point)
 Orthopaedic (0 points) Ear, nose and throat (3 points) Plastics or breast (1 point) Urology (2 points)
 Neurosurgery (4 points) Gastro-intestinal or Hepato-biliary (3 points) Cardiothoracic/ vascular (3 points) Other (0 points)

Indication for surgery:
 Non-communicable disease (0 points) Caesarean section (minus 2 points) Trauma (1 point) Infection (2 points)

Urgency of surgery: Elective (0 points) Urgent (3 points) Emergency (4 points)

Severity of surgery: Minor (0 points) Intermediate (2 points) Major (4 points)

Start of surgery time (24h) & date: h h : m m d d m m 2 0 1 9

ASOS Surgical Risk Score points per risk factor:
 Age + ASA + Surgical procedure category + Indication for surgery + Urgency surgery + Severity surgery = points

Time that the ASOS Surgical Risk Score was calculated: Pre-op Intra-op Immediately post-op

Predicted ASOS Risk Score: Not high-risk patient (<10 points) High-risk patient (≥10 points)

Postoperative Follow Up

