Not high-risk patient: (Indicate postoperative care given): Higher care ward No Yes Increased nursing observations No Yes
Assigned a bed in view of nurses' station No Yes Family with patient in ward No Yes

 High-risk patient: (Indicate all postop surveillance)	Day 0	Day 1	Day 2	Day 3	Day 4+
Higher care ward	 No  Yes				
Increased nursing observations	 No  Yes				
Assigned a bed in view of nurses' station	 No  Yes				
Family with patient in ward	 No  Yes				
'Postoperative surveillance bedside guide' at the patient's bedside?	 No  Yes				

Severe complications (tick all that apply): Superficial or deep surgical site, or body cavity infection N Y Postop day
Bloodstream infection or ARDS N Y Postop day Pneumonia N Y Postop day
Urinary tract or AKI N Y Postop day Postoperative bleed N Y Postop day
Cardiac arrest N Y Postop day Other severe complication N Y Postop day

Days in hospital after surgery

Status at hospital discharge or 30th postoperative in-hospital day: Alive & still in hospital Dead
 Alive & discharged → if alive and discharged, was patient transferred to another facility for higher care? Yes No
If deceased, photo of clinical note of death uploaded Yes CRF completed and verified by..... on dd/mm/2019

ASOS-2 unique patient ID ASOS-2 Trial CRF v4 (Intervention arm)

Patient name: _____ DOB d d m m y y y y

Patient hospital number : _____ ASOS-2 unique patient ID

Appendix 4

ASOS-2 Surgical Risk Calculator Score Card

The ASOS Surgical Risk Calculator Score card

The ASOS Surgical Risk Score is used to identify patients requiring 'increased postoperative surveillance'

How to calculate the ASOS Surgical Risk Score:

1. Calculate score before surgery using the table below
2. ASOS Surgical Risk Score = Age (points) + ASA (points) + Surgery timing (points) + Surgery severity (points) + Indication for surgery (points) + Surgery (points)
3. High-risk patients have ASOS Surgical Risk Score ≥ 10 points
4. A high-risk patient has an ASOS Surgical Risk Score ≥ 10 points
5. If ≥ 10 points, then organize 'increased postoperative surveillance' after surgery

Age	Points
18- 29	0
30-69	+1
≥ 70	+3
ASA	
ASA 1	0
ASA 2	+2
ASA 3	+5
ASA 4 and more	+8
Surgery timing	
Elective surgery	0
Urgent surgery	+3

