3.2. Analysis population

Primary analysis will be by modified intention to treat population which includes all patients recruited from randomised hospitals where the hospital reported any patient data. Hospitals that are randomised, but do not submit any patient data will be excluded from the modified intention to treat analysis on the presumption that there is no risk of exposure to the trial intervention. Patients will be analysed in the treatment group to which their hospitals were originally allocated.

Secondary analyses will include two analytic approaches to two per protocol populations. Refer to table: Secondary analyses based on implementation fidelity. In the first per protocol analysis we will compare all patients from hospitals with data in the standard of care arm to all patients from hospitals with data in the intervention arm where the intervention hospital provided the intervention with fidelity to at least 80% of high-risk patients. Patients from hospitals in the intervention arm where the hospital delivered the intervention with fidelity to fewer than 80% of patients will be excluded from this analysis. In the second per protocol analysis we will compare all patients from hospitals with data in the standard of care arm to all patients from hospitals in the top two tertiles of implementation fidelity. Patients from intervention hospitals in the bottom tertile of implementation fidelity will be excluded from this analysis. At the hospital level we will report implementation fidelity as the proportion of high-risk patients who received the intervention with fidelity. We use two definitions for implementation fidelity; i) provision of at least the high-risk bedside guide plus one additional component of the intervention on days 0 and 1 postoperatively and ii) provision of at least 2 components of the intervention on days 0 and days 1 postoperatively, regardless whether the high-risk bedside guide is one of the components.

Secondary analyses based on implementation fidelity		
	Fidelity = High-risk individuals exposed to the bedside guide plus at least 1 additional component of the intervention	Fidelity = High-risk individuals exposed to at least 2 components of the intervention, regardless whether one is the bedside guide
Intervention hospitals where >= 80% of high-risk patients received the intervention with fidelity	Per protocol analysis 1	Per protocol analysis 3

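### The SAP's missing-outcome sensitivity analysis leaves transfers out of its rule sentence, and its two scenarios cannot bound the relative risk if mortality among the unobserved differs by arm

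*Combined protocol and SAP*

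**What the plan says.** SAP section 3.2.2 (Appendix 6) opens with its scope: "Sensitivity analysis will investigate the potential for unobserved outcomes (transfer out or lost to follow up) to impact primary and secondary effectiveness estimates". The next sentence gives the rule: "individuals with unobserved outcomes (lost to follow up) will alternately be assumed to be alive at discharge (censored at thirty days) or to have died". It uses the primary model and mentions no arm. No arm-specific or tipping-point analysis appears elsewhere in the protocol or SAP.

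Four other places determine how a transferred patient is handled:

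- **CRF (Appendix 3, both arms).** The status item offers three answers: "Status at hospital discharge or 30th postoperative in-hospital day: Alive & still in hospital Dead Alive & discharged". Transfer is a follow-on question to the last of these: "if alive and discharged, was patient transferred to another facility for higher care".
- **Definitions (Appendix 1, hospital resource use).** Status is defined as "The survival status of the patient at hospital discharge, or at the 30 in-hospital day".
- **Protocol section 6.5.** Follow-up ends at that point: "patients will be followed up until discharge or for thirty days whichever is the shorter period".
- **SAP section 3.2, analysis population.** The primary population is "all patients recruited from randomised hospitals where the hospital reported any patient data". The protocol summary (section 2) words it differently: "all participants with a recorded outcome will be analysed according to the treatment group to which they were randomised".

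**The concern.** There are two separate points.

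**Wording.** The scope sentence counts transfers as unobserved, but the parenthesis in the rule sentence drops them. A patient transferred for higher care has a recorded status of alive. A program that looks for missing status will not find that patient, and recoding the patient as dead means overriding a recorded value. The SAP does not say to do so. Programmed literally, the analysis could not show the effect of something it names as a threat.

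**Scenarios.** Setting everyone unobserved to alive, and then everyone to dead, fixes mortality among them at 0% in both arms or 100% in both arms. If that mortality differs between arms, the true relative risk can lie outside the two results. A reader who sees the pair plotted beside the primary estimate could take it as the full range that missing outcomes allow.

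**Working it through.** **Inputs from the documents.** Table 1 (protocol section 7.1) gives 2.0% vs 1.5% mortality, ICC 0.015, CV 0.63, mean cluster size 100, 80% power, two-sided alpha 0.05 and 664 clusters. Section 2 gives about 66,400 patients, which is 33,200 per arm at 1:1.

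**Assumptions.** The share unobserved (m, equal in both arms unless stated) and mortality among the unobserved (q1 intervention, q0 control) are not in the documents. The nearest figure is follow-up above 95% in earlier studies (section 6.5). I therefore show a range up to 5%.

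**Step 1: reproduce the plan's figure.** Two proportions, 2.0% vs 1.5%, need 10,795 per arm. The design effect is 1 + ((1 + 0.63²) × 100 − 1) × 0.015 = 1 + 138.69 × 0.015 = 3.08. Then 10,795 × 3.08 / 100 = 332.5, or 333 clusters per arm and 666 in total, against 664 stated. The sample size is not in dispute, so the same design effect is used below.

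**Step 2: formula.** p1 = 0.015(1 − m) + m·q1 and p0 = 0.020(1 − m) + m·q0. RR = p1/p0. The SE of log RR is √(3.08 × [(1 − p1)/(33,200·p1) + (1 − p0)/(33,200·p0)]), and the limits are RR × exp(±1.96 SE). This approximates the planned GEE.

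**Step 3: what the planned pair does cover.** If mortality among the unobserved is a common q and the shares are m1 and m0, then RR = (a1 + m1·q)/(a0 + m0·q), where a1 and a0 are the observed-death fractions. This is monotone in q, so q = 0 and q = 1 bound it even when m1 and m0 differ. With 2% unobserved in the intervention arm and 1% in control, all-alive gives 0.74 (0.61–0.91), and all-dead gives 0.0347/0.0298 = 1.16 (1.01–1.35). The pair therefore does expose unequal numbers. If transfers are left out of the rule, it cannot do this for transfers.

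**Step 4: what it does not cover.** Equal share unobserved in each arm:

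| Unobserved | Mortality among them (intervention vs control) | p1/p0 | RR (95% CI) |
|---|---|---|---|
| 1% | planned: all alive | 0.01485/0.0198 | 0.75 (0.61–0.92) |
| 1% | planned: all dead | 0.02485/0.0298 | 0.83 (0.71–0.98) |
| 1% | 20% vs 10% | 0.01685/0.0208 | 0.81 (0.67–0.98) |
| 1% | 30% vs 10% | 0.01785/0.0208 | 0.86 (0.71–1.04) |
| 5% | planned: all alive | 0.01425/0.0190 | 0.75 (0.61–0.92) |
| 5% | planned: all dead | 0.06425/0.0690 | 0.93 (0.84–1.03) |
| 5% | 20% vs 5% | 0.02425/0.0215 | 1.13 (0.95–1.34) |

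The 30% vs 10% row at 1% and the 20% vs 5% row at 5% fall outside the planned pair.

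**Step 5: when significance changes.** The share unobserved at which the upper limit reaches 1 is 1.78% for the planned all-dead scenario. Arm-specific pairs with the same ratio compare as follows:

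| Ratio | With 10% in control | With a lower control level |
|---|---|---|
| Twofold | 20% vs 10%: 1.27% | 10% vs 5%: 2.47% |
| Threefold | 30% vs 10%: 0.67% | 9% vs 3%: 2.16% |
| Fourfold | 40% vs 10%: 0.46% | 8% vs 2%: 2.19% |

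In the middle column there is a window below 1.78% in which both planned scenarios stay significant and the arm-specific one does not. In the last column there is none. At the extreme (100% vs 0%), significance is lost from 0.14%, about 47 patients per arm. Below that share, no arm-specific assumption removes it.

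**The case against.** On wording, the rule sentence applies to individuals with unobserved outcomes, a term that the sentence before it has just defined to include transfers. A reader might infer that the SAP deliberately excludes transfers from the sensitivity analysis; the text does not support that. This stands, and it makes the first point close to editorial. What remains is that transfers carry a recorded live status, so a programmer needs an explicit instruction.

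A reader might also infer that the primary result is compromised. It is not. The outcome is in-hospital death with follow-up to discharge or day 30, so a patient who leaves alive has an observed status for that outcome. The CRF, the definitions and the SAP population favour counting transfers as survivors in the primary model. The protocol summary's restriction to recorded outcomes, read with the SAP calling transfers unobserved, leaves this short of settled.

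On the scenarios, the planned pair is pre-specified, uses the primary model and is plotted beside the main estimate. The SAP never claims that it bounds every mechanism. The documents give no reason to expect mortality among the unobserved to differ by arm, nor a direction. All of that is fair, and it is why the grid supplements the pair and does not replace it.

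Two further inferences fail. One is that any two- to fourfold difference in mortality overturns a significant result; step 5 shows that this depends on the absolute levels. The other is that the point has little effect once all-dead has already lost significance; at 5% unobserved the estimate can still move to 1.13, well beyond 0.93.

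**Conclusion.** The point holds as a minor one. The wording gap is real but is a clarification. The substantive limit is that the two scenarios bound the relative risk only when mortality among the unobserved is the same in both arms.

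The figures are illustrations, not forecasts. They rest on assumed unobserved shares and mortalities, observed rates exactly at the design values, equal shares by arm in steps 4 and 5, and a design-effect approximation to the GEE. If transfers and losses prove very rare, the scenario point has no practical effect on significance. Nothing here calls the primary analysis, the design or the sample size into question.

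**What to change.** Keep both planned scenarios, and make three changes to SAP section 3.2.2.

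1. In the rule sentence, name transfers out alongside losses, and state that patients recorded as transferred are recoded in both scenarios. Note that the CRF item captures only transfers for higher care, so other transfers cannot be identified from it and would remain survivors.
2. Add a tipping-point grid under the primary model, varying mortality among the unobserved independently by arm. Report the relative risk and confidence interval across the grid, and the pairs at which the interval reaches 1.
3. Report transfers and losses by arm, so that readers can see whether the trial lies in a range where this matters.

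The cost is a few words and a few extra model runs on data already collected. The downside is that an all-dead assumption may count appropriate escalation of care as failure, so these should remain sensitivity analyses only. If transfers and losses are rare, the grid will add little.
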